7.7.6 Clinical Laboratory Evaluations

7.7.6.1 Laboratory Abnormalities

Laboratory abnormalities are determined from laboratory measurements analyzed at the central or local laboratory.

Three types of laboratory summaries are produced by treatment and total for on-treatment period:

- Worst grade of laboratory value on treatment (0, 1, 2, 3, 4, 3-4),
- Treatment emergent abnormalities (not emergent, 1, 2, 3, 4, 3-4),
- Change from baseline to worst grade on treatment (0, 1, 2, 3, 4, and not reported, for baseline and on-study).

Worst grade of emergent laboratory abnormalities are summarized by treatment and total for on-treatment period. Treatment emergent abnormalities are abnormalities that worsened relative to baseline (including missing baseline). The “not emergent” category in this table is for subjects whose laboratory grades did not increase from baseline.

Laboratory abnormalities are further summarized by baseline toxicity grade: “0,” “1-2,” “3-4” or “Not reported” versus worst on-study grade “0,” “1-2,” “3-4” or “Not Reported.” These analyses are done by treatment.

Commonly collected laboratory tests with CTCAE grades may include, but are not limited to, the following:

- Hematology: hemoglobin, Hematocrit, WBC count with differential to calculate absolute lymphocyte count, platelets; CD4+, CD8+ T-Cell Count and CD4+/CD8+ ratio
- Serum Chemistry: Sodium, Potassium, Chloride, Bicarbonate, Blood Urea Nitrogen (BUN), Creatinine, Glucose, ALT, AST, total bilirubin (reflex to Direct bilirubin), Alkaline phosphatase, Lactate dehydrogenase (LDH), Total Protein, Albumin, Calcium, Phosphorus, Magnesium, Amylase and Lipase
- Thyroid Function Test: TSH (reflex to Free T3 and Free T4)

A by-subject listing of these laboratory parameters will be provided. Laboratory abnormality criteria and laboratory results outside of normal range will be listed.

7.7.6.2 *Laboratory Tests over Time*

Laboratory values are summarized at baseline and each scheduled visit week on treatment for treated subjects using observed values. This summary is done by treatment group and total. A similar analysis is done for change from baseline laboratory values. Commonly collected laboratory tests may include, but are not limited to, the following:

- Hematology: hemoglobin, Hematocrit, WBC count with differential to calculate absolute lymphocyte count, platelets, , CD4+, CD8+ T-Cell Count and CD4+/CD8+ ratio
- Serum Chemistry: Sodium, Potassium, Chloride, Bicarbonate, Blood Urea Nitrogen (BUN), Creatinine, Glucose, ALT, AST, total bilirubin (reflex to Direct bilirubin), Alkaline phosphatase, Lactate dehydrogenase (LDH), Total Protein, Albumin, Calcium, Phosphorus, Magnesium, Amylase and Lipase
- Thyroid Function Test: TSH (reflex to Free T3 and Free T4)

7.7.6.3 *Select Laboratory Test Results*

The number of subjects who meet the following laboratory-defined criteria for potential drug induced liver injury (pDILI) during on-treatment period will be summarized by treatment and total:

- AT (ALT or AST) elevation > 3 times upper limit of normal (ULN)
AND
- Concurrent Total bilirubin > 2 times ULN. Concurrent is defined as elevation of total bilirubin within 3 days of the AT elevation.

7.7 *Vital Signs and other Safety Evaluation*

7.7.7.1 *Vital signs*

Vital signs parameters (systolic blood pressure, diastolic blood pressure, heart rate, respiratory rate and body temperature) will be listed. Summaries of vital sign parameters will be provided for each vital sign parameter at corresponding visits by treatment for each scheduled visit.

ECG

All recorded ECGs values will be listed.

If QTcF is not available in the database, QTcF will be calculated using the reported uncorrected QT Interval and Heart Rate, and the following formula:

$$\text{QTcF} = \text{QT}/(60 / \text{HEART RATE})^{1/3}$$

Summaries of ECG parameters (heart rate (HR), QT (QT, QTcF), PR and QRS intervals) will be tabulated by study day and treatment. Summaries of ECG parameters will include change from baseline at listed time points.

Subjects with ECG intervals outside of a pre-specified range will also be summarized. The following criteria will be used to determine ECG results that are outside of a pre-specified range:

PR (msec): Value > 200

QRS (msec): Value > 120

QT (msec): Value > 500 or change from baseline > 30

QTcF (msec): Value > 450 or change from baseline > 30

QTcF (msec): Value > 500 or change from baseline > 60

Physical examination

Physical examination findings will be listed.

7.7.8 *Immunogenicity*

ADA Status of a Sample:

- ADA Positive Sample: ADA is detected
- ADA Positive Relative to Baseline Sample: After initiation of treatment, (1) an ADA positive sample in a participant who is baseline ADA negative or missing but with sample confirmed as specific against nivolumab (2) an ADA positive sample with ADA titer to be at least 4-fold or greater (\geq) than baseline positive titer
- ADA Negative Sample: No ADA detected.

ADA Status of a Participant:

- Baseline ADA Positive Participant without on treatment boost: A participant with baseline ADA positive sample with no titer increase \geq 4 fold following initiation of treatment
- ADA Positive Participant: Participant is counted as ADA positive if after initiation of treatment, has a ADA positive relative to baseline sample. The samples in the following definitions below refer to post-dose samples only
- Persistent Positive Participant: ADA positive relative to baseline sample at 2 or more sequential time points, where the first and last ADA positive relative to baseline samples are at least 8 weeks apart.
- Only the Last Sample Positive Participant: Not persistent but ADA positive relative to baseline sample in the last sampling time point
- Other Positive Participant: Not persistent but some ADA positive relative to baseline samples with the last sample being not ADA positive relative to baseline sample
- ADA Negative Participant: A participant with no ADA positive sample at any time

The number and percentage of participants with positive ADA samples in each of the ADA Positive Participant subgroups will be summarized by treatment and by time. A by-participant listing will be provided with corresponding antibody titer values.

A summary table for the incidence of different types of ADA positive participants will be provided by treatment.

7.8 Pharmacokinetics

Pharmacokinetics parameters as defined in the primary endpoint section ([Section 4.1](#)) will be derived using serum concentration versus time, as data allow.

Individual subject pharmacokinetic parameter values will be derived by non compartmental methods using a validated pharmacokinetic analysis program. Actual times will be used for the analyses.

Subject serum concentration-time profiles will be listed and summarized by treatment and nominal collection time. Plots of individual serum concentration profiles over time will be provided. Overlays of individual serum concentration profiles over time will be provided by treatment. Plots of mean (+SD) serum concentration profiles versus nominal time will be presented, and both treatments will be superimposed on the same plot.

All individual PK parameters will be listed including any exclusions and reasons for exclusion from summaries. Summary statistics will be tabulated for each PK parameter by treatment. Geometric means and coefficients of variation will be presented for Cmax, Cmin, Cavg, AUC(0-T), CLT, and Vd. Median and range will be presented for Tmax. Mean and standard deviation will be presented for T_{1/2}. Scatter plots of Cmax, Cmin Cavg and AUC(0-T) versus dose will be provided.

7.9 Biomarker Analyses

Summary statistics of PD-1 receptor occupancy levels will be tabulated by treatment and time. Profile plots will be provided.

Summary statistics for pharmacodynamic marker (mHLA-DR expression, absolute lymphocyte count) assessments and corresponding changes (or percent changes) from baseline will be tabulated by treatment and time. Possible association between changes in pharmacodynamic measures of interest and nivolumab exposure may be explored graphically, when appropriate.

8 CONVENTIONS

Presentations follow BMS general global standards for all data domains.² This document is available upon request.

8.1 Visit Window

Windows are constructed for each visit in order to slot data. Labels for study periods and visits appear in listings and datasets.

Time is measured from the dose date of study therapy. For longitudinal summaries of data, windows around planned measurement times are based on the midpoint between planned study visits unless specified otherwise.²

Study day is defined as the difference between the measurement date and dose date of study therapy.²

Visits are defined below in Table 8.1-1. Windows are constructed for each visit in order to slot data. Labels for study periods and visits appear in listings and datasets.

Table 8.1-1: Visit Definitions

Study Period Label	Visit Label	Visit Number	Target Day from Start of Study Period	Visit Window
PRE-TREAT	PRE-TREAT	1	1	< 1 day ^a
ON-TREAT	DAY 1	2	1	1 - 4 days ^b or 1-2 days ^c or day 1 ^d
	DAY 2	3	2	day 2 ^d
	DAY 3	4	3	day 3 ^d
	DAY 4	5	4	day 4 ^d or 3-5 days ^c
	DAY 5	6	5	day 5 ^d
	DAY 6	7	6	day 6 ^d
	DAY 7	8	7	day 7 ^d or 6-8 days ^c
	WEEK 2- DAY 10	9	10	5 - 11 days ^b or 9-11 days ^c or 8 -11 days ^d
	WEEK 2- DAY 14	10	14	12 - 17 days
	WEEK 3 - DAY 21	11	21	18 - 24 days
	WEEK 4 - DAY 28	12	28	25 - 35 days
	WEEK 6 - DAY 42	13	42	36 - 49 days
	WEEK 8 - DAY 56	14	56	50 - 63 days
	WEEK 10 - DAY 70	15	70	64 - 80 days
	INDEX HOSPITALIZATION DISCHARGE	16	-	-
	STUDY DISCHARGE - DAY 90	17	90	≥ 81 days

^a See Section 6.1, Study Periods, for classification of measurements on Day 1 (active study therapy) as pre-treatment or on-treatment depending on the data domain.

^b For measurements to be assessed only on Day 1 during the first week.

^c For measurements to be assessed on Day 1, Day 4 and Day 7 during the first week.

^d For measurements to be assessed daily during the first week.

^c For measurements to be assessed on Day 10, Day 14, Day 21 and Day 28 during Week 2 - Week 4.

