**Table 2.-1: Screening Procedural Outline (CA209923)**

Procedure	Screening a Visit	Baseline b Visit	Notes
Follicle Stimulating Hormone (FSH)	X		Women only. Refer to Appendix 4 for applicability.
Thyroid function testing		X	See note in Section 9.4.4
Adverse Event Reporting			
Monitor for Serious Adverse Events (SAEs)	X	X	Collection of SAEs begins when the informed consent form is signed.
Clinical Drug Supplies			
Randomize		X	Randomization can occur either on Day -1 or Day 1.
Clinical Assessments			
SOFA Score		X	Pre-dose, after participant is admitted to the ICU
Ventilator Usage		X	Record Start date, if applicable
Vasopressor Usage		X	Record Start date, if applicable
Dialysis Usage		X	Record Start date, if applicable

a Screening assessments must be performed within 10 days prior to Day 1 administration of randomized study treatment. If screening assessments other than labs are within 24 hours of dosing, then assessments performed for screening can be counted as both screening and baseline. Screening labs within 48 hours prior to dosing can be counted as both screening and baseline.

b Baseline assessments excluding labs must be within 24 hours prior to dosing. Baseline labs can be within 48 hours prior to dosing.

Procedure	WK 1 D1-7	WK2 D10	WK2 D14	WK3 D21	WK4 D28	WK6 D42	WK8 D56	WK10 D70	Indexa Hospitaliza tion Discharge	Studyb Discharge D90	Notes
Visit window		+/- 1 day	+/- 1 day	+/- 2 days	+/- 3 days	+/- 4 days	+/- 5 days	+/- 7 days		+/- 9 days	
Clinical Drug Supplies											
Randomize	X										Randomization can occur either on Day -1 or Day 1.
Study Drug Administration	X										Day 1.
Safety Assessments											
Physical Examination (PE)	X		X		X		X		X	X	Perform daily in Week 1, at Index Hospitalization Discharge, and at Study Discharge; Perform at other time points only if still hospitalized.
Physical Measurements									X	X	Weight only.
Vital Signs	X		X		X		X		X	X	Perform daily in Week 1, at Index Hospitalization Discharge, and at Study Discharge; Perform at other time points only if still hospitalized. See note in screening

Table 2.-2: On Treatment Procedural Outline (CA209923)											

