Procedure	WK 1 D1-7	WK2 D10	WK2 D14	WK3 D21	WK4 D28	WK6 D42	WK8 D56	WK10 D70	Indexa Hospitaliza tion Discharge	Studyb Discharge D90	Notes
											procedures.
Electrocardiogram (ECGs)	X		X		X		X		X	X	Perform at end of infusion on Day 1, at Index Hospitalization Discharge, and at Study Discharge; Perform at other time points only if still hospitalized.
Clinical safety laboratory tests	X	X	X	X	X		X		X	X	Days 1, 4 and 7 of week 1. See note in screening procedures and in Section 9.4.4
Pregnancy Test					X		X			X	WOCBP only. See note in Section 9.4.4.
Thyroid function testing							X		X	X	See note in Section 9.4.4
Adverse Event Reporting											
Monitor for Non-Serious Adverse Events	Collection of nonserious adverse events begins at initiation of study treatment. Adverse events must be collected up to Day 90.										
Monitor for Serious Adverse Events	See note in Screening procedures. SAEs must be collected up to Day 90.										
Other Assessments											

Table 2.-2: On Treatment Procedural Outline (CA209923)											
Procedure	WK 1 D1-7	WK2 D10	WK2 D14	WK3 D21	WK4 D28	WK6 D42	WK8 D56	WK10 D70	Indexa Hospitaliza tion Discharge	Studyb Discharge D90	Notes
Ventilator Usage	In days counting from the day of study treatment administration during participant’s index hospitalization.										
Vasopressor Usage	In days counting from the day of study treatment administration during participant’s index hospitalization.										
Dialysis Usage	In days counting from the day of study treatment administration during participant’s index hospitalization.										
Mortality	Date and primary cause of death.										
SOFA Score	Daily during the first week after study treatment administration, and weekly thereafter while participant is in ICU during participant’s index hospitalization.										
Length of ICU stay During Index Hospitalization	ICU discharge date during index hospitalization.										
Length of Index Hospitalization	Hospital discharge date during index hospitalization.										
Pharmacokinetic (PK) and Immunogenicity Assessments	See Section 9.5 for details and collection schedule.										

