6 STUDY PERIODS, TREATMENT REGIMENS AND POPULATIONS FOR ANALYSES

6.1 Study Periods

This study consists two periods: pre-treatment and on-treatment.

The pre-treatment period begins with screening and extends until study drug administration on Day 1.

Measurements taken before Day 1 are considered pre-treatment for all data domains. In addition, measurements taken on Day 1 are considered pre-treatment for the following data domains: demography, SNP, medical history, physical measurements, inclusion/exclusion, and patient reported outcomes.

The on-treatment period begins with study drug administration on Day 1 and ends approximately 90 days after the dose date. It is expected that minimal drug exposure and undetectable drug levels will be present beyond 90 days post-dose.

Measurements taken after Day 1 through approximately Day 90 are considered on-treatment for all data domains. In addition, measurements taken on Day 1 are considered on-treatment for the following data domains: AEs, drug dispensation, exposure.

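### SAP 8.1 counts the dosing day as study day 0, but Table 8.1-1, SAP 6.1 and the protocol count it as Day 1; read literally, week-1 vital signs and the end-of-infusion ECG are mis-slotted

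*SAP*

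**What the plan says.** SAP 8.1 (Visit Window) gives the rule: "Study day is defined as the difference between the measurement date and dose date of study therapy". It also says that "windows around planned measurement times are based on the midpoint between planned study visits unless specified otherwise". A superscript on the study-day sentence cites a sponsor standard that is not among the documents.

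Table 8.1-1 in the same section assigns values below 1 to PRE-TREAT, gives DAY 1 a target day of 1, and starts every DAY 1 window at 1. Its footnote a reads: "See Section 6.1, Study Periods, for classification of measurements on Day 1 (active study therapy) as pre-treatment or on-treatment depending on the data domain".

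SAP 6.1 states: "The on-treatment period begins with study drug administration on Day 1 and ends approximately 90 days after the dose date". It then lists domains for Day 1 itself: "measurements taken on Day 1 are considered on-treatment for the following data domains: AEs, drug dispensation, exposure". A second list names the domains that are pre-treatment on Day 1. Neither list contains ECG, vital signs, laboratory tests or SOFA.

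Protocol Table 2.-2 schedules vital signs as follows: "Perform daily in Week 1, at Index Hospitalization Discharge, and at Study Discharge; Perform at other time points only if still hospitalized". For ECG it says: "Perform at end of infusion on Day 1, at Index Hospitalization Discharge, and at Study Discharge". Under Protocol Table 2.-1, footnote b, "Baseline assessments excluding labs must be within 24 hours prior to dosing"; laboratory tests have 48 hours. Baseline values can therefore fall on Day 1 before the infusion.

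**The concern.** A date minus itself is 0, so under the SAP 8.1 sentence the dosing day is 0 and the day after is 1. The table that uses this number is built for a dosing day of 1. A programmer who follows the sentence would shift every daily week-1 measurement one label early and would find no on-treatment window for anything measured on the dosing day.

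The SAP summarises vital signs for each scheduled visit and ECG change from baseline by time point, by dose group. The DAY 1 vital-sign row would hold Day 2 values and the DAY 7 row would have no planned value. The DAY 1 ECG row, meant to show the change right after the infusion, would also have no planned value.

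**Working it through.** **1. Which convention do the documents use?** Protocol Table 9.5-1 gives hours from the start of infusion. The Day 1 convention implies hours = (day − 1) × 24:

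- Day 2: 1 × 24 = 24
- Day 28: 27 × 24 = 648
- Day 90: 89 × 24 = 2136

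All 15 numbered days in that table satisfy the formula. SAP 6.1 also places dosing on Day 1.

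**2. Does Table 8.1-1 follow it?** SAP 8.1 bases windows on midpoints between planned visits. Each multi-day window's last day is compared with the midpoint on each scale:

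| Boundary (last day of window) | Midpoint, dosing day = 1 | Midpoint, dosing day = 0 | Fits |
|---|---|---|---|
| footnote b, 4 | 5.5 | 4.5 | day 0 |
| footnote c, 2 | 2.5 | 1.5 | Day 1 |
| footnote c, 5 | 5.5 | 4.5 | Day 1 |
| footnote c, 8 | 8.5 | 7.5 | Day 1 |
| footnote d, 7 | 8.5 | 7.5 | day 0 |
| 11 | 12 | 11 | day 0 (tie to earlier visit) |
| 17 | 17.5 | 16.5 | Day 1 |
| 24 | 24.5 | 23.5 | Day 1 |
| 35 | 35 | 34 | Day 1 (tie to earlier visit) |
| 49 | 49 | 48 | Day 1 (tie to earlier visit) |
| 63 | 63 | 62 | Day 1 (tie to earlier visit) |
| 80 | 80 | 79 | Day 1 (tie to earlier visit) |

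Nine of 12 boundaries fit only the Day 1 scale. Three fit day 0, counting 11/12 under the tie rule that the table uses at 35, 49, 63 and 80. The table is mainly on the Day 1 scale, and the study-day sentence is the text out of line.

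**3. Week 1 under the literal rule.** Protocol day d gets study day d − 1.

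- Vital signs (one-day windows, footnote d): Day 2 → DAY 1, 3 → DAY 2, 4 → DAY 3, 5 → DAY 4, 6 → DAY 5, 7 → DAY 6. All 6 are one label early. DAY 7 is fed only by Day 8, when none are planned.
- ECG (window 1 to 4, footnote b): end of infusion on Day 1 → 0. The table's window below 1 would make it PRE-TREAT, SAP 6.1 makes it on-treatment, and no on-treatment window contains 0. The DAY 1 row is fed only by Days 2 to 5, when no ECG is planned. If an infusion crossed midnight, the difference would be 1 and the ECG would fall in DAY 1.
- Laboratory tests (footnote c): Day 4 → 3, in the 3-to-5 window; Day 7 → 6, in the 6-to-8 window. Both are correct.
- Day 1 laboratory tests and vital signs → 0 → PRE-TREAT. This is wrong only for values taken after dosing began, and the schedule does not say when they are taken.
- SOFA: if the first week means Days 1 to 7, it shifts as vital signs do. If it means dose date +1 to +7, the plain difference gives 1 to 7 and the labels DAY 1 to DAY 7.

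**4. Day 10 onward.** Planned visit days with the protocol's visit windows:

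- Laboratory tests at 10±1, 14±1, 21±2, 28±3, 56±5, 90±9: 3 + 3 + 5 + 7 + 11 + 19 = 48 permitted days. Misplaced: Day 9 (→ 8, DAY 7), Day 25 (→ 24, DAY 21), Day 81 (→ 80, DAY 70). That is 3 of 48.
- ECG and vital signs at 14±1, 28±3, 56±5, 90±9: 3 + 7 + 11 + 19 = 40 permitted days. Misplaced: 25 and 81. That is 2 of 40.
- No target day moves. Day 64 would move to DAY 56, but only PK is scheduled at Day 70, and PK concentrations are summarised by nominal time.

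**5. With +1 on and after the dose date.** Days 1 to 7 and every later planned day fall in their own windows, the end-of-infusion ECG falls in DAY 1, and the counts in step 4 become 0 of 48 and 0 of 40. Pre-dose values taken on Day 1 now also get study day 1, so the +1 alone would put them in ON-TREAT DAY 1. That needs its own rule.

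**The case against.** The strongest reply is that nobody would program it this way. The sentence cites a sponsor standard, SAP 8.2 refers ECG, laboratory and vital-sign derivations to internal documents, and footnote a ties the table's Day 1 to the day of active therapy. The intended convention can be inferred, so only a wording fault is shown.

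Most of this stands, and it is why the point is minor. It does not cure the sentence. The citation is attached to the plain-difference wording itself, so a reader would expect the standard to say the same. Footnote a defers to SAP 6.1, whose Day 1 lists omit ECG, vital signs, laboratory tests and SOFA. The three boundaries that fit day 0 show that the table was not built on one convention throughout.

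A second objection concerns SOFA, and it is accepted. The protocol's phrase for the first week after treatment allows either set of days, and SAP 7.6.1 does not cite Table 8.1-1, so the SOFA shift is conditional.

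A reader might go further and infer that the tables will be wrong, or that the end-of-infusion ECG will be treated as a baseline value. The documents do not support either. The standard is not available, and the SAP 6.1 period rule makes that ECG on-treatment. What is shown is two rules that disagree.

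**Conclusion.** The point holds as a contradiction within SAP 8.1, and between it and SAP 6.1 and the protocol. Its size if the sentence is followed:

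- all six vital-sign days from Day 2 to Day 7 are labelled one day early;
- two rows (DAY 7 vital signs, DAY 1 ECG) have no planned value;
- from Day 10 on, only early-edge days move.

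Adverse events, drug dispensation and exposure are settled by SAP 6.1, and PK concentrations by nominal time, so none of these is affected. The affected outputs are descriptive and the harm is mislabelled rows: minor. The conclusion assumes that Table 8.1-1 is applied to the study day as SAP 8.1 defines it, and that the infusion does not cross midnight.

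**What to change.** In SAP 8.1, define study day as measurement date − dose date + 1 on or after the dose date, and as measurement date − dose date before it.

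Add a rule for domains absent from the SAP 6.1 Day 1 lists (ECG, vital signs, laboratory tests, SOFA). Values before the start of infusion on Day 1 are PRE-TREAT and may serve as baseline. Values at or after the start of infusion, including the end-of-infusion ECG, are ON-TREAT DAY 1.

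State which days the first week of SOFA covers. If it is dose date +1 to +7, the last value is study day 8 under the corrected rule and falls in the daily-measure window 8 to 11, labelled Day 10.

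The cost is a few sentences. The windows in Table 8.1-1 need no change and no visit or assessment is added. The Day 1 rule needs a clock time or a pre-dose/post-dose flag for Day 1 values. The documents do not show whether the case report form holds one for every domain, so this should be checked before programming.
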